	
 Mean/median changes in visual acuity score from Screening to lowest score during Days 1-15. Frequency of participants with any new color vision abnormalities (tritan, protan, deutan) in one or both eyes and degree of severity (mild, moderate, severe).
Assess the impact on heart rate (HR), blood pressure (BP) and electrocardiogram (ECG) profile of each dose regimen of TBA-7371 and of HRZE over the 14-day treatment period.	
From Day 1 through Day 15:
 
 Mean and frequency distribution of changes in heart rate (HR), systolic blood pressure (SBP) and diastolic blood pressure (DBP) as measured by the following 2 (BP) or 3 (HR) methods: 
 Manual HR, SBP and DBP from vital signs, after at least 1 minute in supine position (“manual, supine”); Manual HR, SBP and DBP from vital signs, after 2 (± 0.5) minutes in standing position (“manual, 2-minute standing”); HR from ECG, supine position (“ECG, supine”) Frequency of participants with $\geq 25\%$ increase in HR, decrease in SBP, decrease in DBP vs. baseline as measured with any of the methods described above. Mean and frequency distribution of percentage of days with $\geq 25\%$ increase in HR, decrease in SBP, decrease in DBP vs. baseline. 
Mean/median change from Screening through Day 15 in PR, RR, QRS, QT, and QTcF interval values from baseline ECG.

Assess whether there is tachyphylaxis over the 14-day treatment period for HR, SBP, DBP and eye symptoms	
 Mean change in HR, SBP, and DBP from Day 1 to Days 4, 7, 10, 14, and 15 for each of 2 BP and 3 HR measurement methods described above. Change in frequency of participants with eye symptoms (all, severe, serious) and change in worst visual acuity score and frequency of color vision abnormalities (tritan, protan, deutan) in one or both eyes and degree of severity (mild, moderate, and severe) from Day 1 to Days 4, 7, 10, 14, and 15.
Assess whether cardiovascular and/or ophthalmic adverse events persist or recur up to 4 weeks after discontinuation of treatment with TBA-7371.	
 Mean change in HR, SBP, and DBP from Baseline to Days 28 and 42 and from Day 14 to Days 28 and 42 as measured by the following 2 (BP) or 3 (HR) methods: 
 Manual HR, SBP and DBP from vital signs, after at least 10 minutes in supine position (“manual, supine”);

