9.2 Definitions

Screening EBA Measure: Average of the EBA measurements (i.e., log CFU, TTP in MGIT, and log concentration of sputum LAM) from the day -2 and day -1 overnight sputum samples of the screening phase will be used to determine the screening EBA measurement. If one of the overnight sputum samples is missing, the single non-missing sample will be directly used as the screening EBA measurement.

Baseline definition for other efficacy and safety variables: The last assessment made prior to the first administered dose of study intervention will be considered baseline for analysis purposes. Baseline values of ECG and vital signs are measured on Day 1 before the first dose of study medication is administered.

Day 1: Study day 1 is the day of first administration of TBA-7371 or HRZE. Positive study days will be counted forward from Day 1. Day -1 will be the date immediately preceding Day 1, and negative study days will be counted backward from Day 1.

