12.5 Vital Signs

12.5.1 Intraday Vital Signs Results

Intraday values of vital signs (HR, SBP, and DBP) measured while in supine and while in standing at predose, and 2.5h, 10.5h, and 16.5h after the time of 1st daily dose of study drug on Days 1, 4, 7, 10, and 14 and changes from predose taken on the same day will be summarized using descriptive statistics by treatment group. Line plots of mean of intraday HR, SBP, and DBP measured while in supine and while in standing by treatment group will be provided.

Potentially clinically important criteria of intraday changes from presdose in HR, SBP, and DBP while measured in supine and while in standing are defined as follows:

- $\geq 25\%$ increase in supine HR
- $\geq 25\%$ increase in standing HR
- $\geq 25\%$ decrease in supine SBP
- $\geq 25\%$ decrease in standing SBP
- $\geq 25\%$ decrease in supine DBP
- $\geq 25\%$ decrease in standing DBP

For each of the criteria, the frequency and proportion (expressed in percent) of participants who met the criterion at each time point will be provided by treatment group. For the by-time point summary, the denominator for the proportion is the number of participants in the treatment group with non-missing values at predose and the given post-predose time point taken on the same day.

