12.6 Electrocardiogram

12.6.1 Intraday ECG Results

Intraday values of ECG variables (HR, QRS duration, RR, PR, QT, and QTcF intervals) measured at predose, and 2.5h, 10.5h, and 16.5h after the time of 1st daily dose of study drug on Days 1, 4, 7, 10, and 14 and changes from predose taken on the same day will be summarized using descriptive statistics by treatment group.

Potentially clinically important criteria for QTcF are defined as follows:

- Observed: 451 to 480, 481 to 500, and >500 msec
- Change from predose taken on the same day: 31 to 60, and >60 msec

For each of the criteria, the frequency and proportion (expressed in percent) of participants who met the criterion at each time point will be provided by treatment group. For the by-time point summary, the denominator for the proportion is the number of participants in the treatment group with non-missing values at predose and the given post-predose time point taken on the same day.

Additionally, intraday value of ECG variables for sex subgroup (female and male) will be summarized similarly as described above. Boxplots of intraday values of QTcF by treatment group and sex will be provided.

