12.6.2 Daily ECG Results

Values of ECG variables (HR, QRS duration, RR, PR, QT, and QTcF intervals) measured at baseline (Day 1 predose), Days 4 (predose), 7 (predose), 10 (predose), 14 (predose), 15, 28, and 42 and changes from baseline will be summarized using descriptive statistics by treatment group.

Potentially clinically important criteria for QTcF are defined as follows:

- Observed: 451 to 480, 481 to 500, and >500 msec
- Change from baseline: 31 to 60, and >60 msec

For each of the criteria, the frequency and proportion (expressed in percent) of participants who met the criterion at each time point will be provided by treatment group. For the by-time point summary, the denominator for the proportion is the number of participants in the treatment group with non-missing values at baseline and the given post-baseline time point.

Additionally, values of ECG variables for sex subgroup (female and male) will be summarized similarly as described above. Boxplots of daily values of QTcF by treatment group and sex will be provided.

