 - EWV: vital signs and BW if the participant withdraws from the study between Day 1 and 14.At each time point BT, RR and BW will be measured once, whereas HR, SBP and DBP will be measured twice as follows: after 10 min supine ("manual, supine") and after 2 (± 0.5) min standing ("manual, 2-min standing"). When ECG, vital signs and/or blood/serum samples are to be obtained at the same time point, the following order must be followed: ECG, vital signs, blood/serum sample, within 5 min of each other.
9. **ECG recording.** 12-lead ECG will be recorded once at each time point after at least 10 minutes of supine rest as follows:
 - Screening Phase: once in the morning at approximately the same time the 1st daily dose study drug will be administered.
 - Study Treatment Phase: on Days 1, 4, 7, 10 and 14 before administration of the 1st daily dose of study drug and 2.5h, 10.5h and 16.5h thereafter (see Table 4 of the protocol).
 - Follow-up Phase: on Day 15 in the morning before 1st daily dose of standard of care medication; on Days 28 and 42 during the visit.

TBA-7371

Statistical Analysis Plan: Gates MRI-TBD03-201

Bill & Melinda Gates Medical Research Institute

04-October-2022

- EWV: if the participant withdraws from the study between Day 1 and 14.

10. Eye assessment. A trained staff member will assess: i) eye symptoms using a standardized script (Section 10.5, Appendix 5 of the protocol), ii) visual acuity by means of the Rosenbaum Pocket Eye Screener, iii) color vision by means of the Waggoner Computerized Color Vision Test and as follows:

- Screening Phase: once in the AM.
- Study Treatment Phase: Days 1, 4, 7, 10, and 14, 2.5h after 1st daily dose of study drug (see Table 4 of the protocol).
- Follow-up Phase: Days 15, 28 and 42 during the visit.
- EWV: if the participant withdraws from the study between Days 1 and 14.

11. Study drug (IMP) administration. Study drug (TBA-7371 or HRZE) will be administered from Day 1 to Day 14 based on the randomization list by an authorized and trained site staff member. The 1st dose of study drug will be administered at the same time each Day for the individual participant. Subsequent doses will be administered as follows (see Table 4 of the protocol):

- Twice daily (BID) schedules: 12h after 1st dose
- Three times (TID) daily schedule: 7h and 14h after 1st dose

Fasting must occur at least 2 hours before dosing and at least 1 hour after dosing. Study drug administration will be followed by 200 mL water.

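### After Day 1, no table compares a post-dose heart rate, blood pressure or ECG reading with baseline, so the 25% and QTcF change counts can miss or under-classify changes

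*SAP*

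**What the plan says.** SAP 9.2 fixes the reference: "Baseline values of ECG and vital signs are measured on Day 1 before the first dose of study medication is administered". The secondary endpoints in SAP 5.2 and 6.4, and in Protocol 3.2, are built on it. They include the participants whose HR rises, or whose SBP or DBP falls, by 25% or more against baseline; the percentage of days on which that happens; and the mean and median change through Day 15 in PR, RR, QRS, "QT, and QTcF interval values from baseline ECG".

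ECGs are recorded "on Days 1, 4, 7, 10 and 14 before administration of the 1st daily dose of study drug and 2.5h, 10.5h and 16.5h thereafter" (SAP Appendix 1). The vital-sign footnote gives the same times.

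The analysis sections split these readings in two.

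- **Intraday tables.** For ECG (SAP 12.6.1), values "on Days 1, 4, 7, 10, and 14 and changes from predose taken on the same day will be summarized", and the QTcF change categories are "Change from predose taken on the same day: 31 to 60, and >60 msec". For HR, SBP and DBP (SAP 12.5.1), "changes from predose taken on the same day will be summarized using descriptive statistics by treatment group", and the 25% criteria are defined on that same-day change.
- **Daily tables.** For ECG (SAP 12.6.2), values are those "measured at baseline (Day 1 predose), Days 4 (predose), 7 (predose), 10 (predose), 14 (predose), 15, 28, and 42 and changes from baseline", with categories "Change from baseline: 31 to 60, and >60 msec". SAP 12.5.2 does the same for vital signs and adds the number of days on which each criterion is met.

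SAP 12.6.1 also counts observed QTcF of 451 to 480, 481 to 500 and over 500 ms at each time point. SAP section 8 reports no departure from the protocol's analyses.

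**The concern.** From Day 4 on, the morning pre-dose reading is itself taken on treatment. Using it as the reference subtracts whatever effect remains from earlier doses. The daily tables do not make up for this, because on treatment days they hold only pre-dose readings. The endpoint defined against baseline is therefore not evaluated at the times the trial samples after dosing, except on Day 1.

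The heart rate and blood pressure part matters most. Protocol 2.3 names heart rate increase with blood pressure decrease among the most common treatment-emergent events in the healthy-volunteer trial. Protocol 2.3 and 4.2 also say that the BID and TID schedules are there to see whether splitting the dose improves tolerability. A reference reading whose distance from the last dose differs by schedule is a poor basis for that comparison.

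**Working it through.** The plan states no figure for this point, so there is none to reproduce. The check is a count, an identity and two worked records.

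**1. Count of time points** (SAP Appendix 1). 5 days × 3 post-dose times = 15 per participant. On Day 1 the same-day pre-dose reading is the baseline, so 3 of the 15 are covered. On Days 4, 7, 10 and 14, 4 × 3 = 12 are compared only with that day's pre-dose value.

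**2. Identity.** Let B be the Day 1 pre-dose value, P the same-day pre-dose value and X the post-dose value.

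- Differences: X − B = (X − P) + (P − B). The intraday table holds the first term and the daily table the second. Neither holds the sum.
- Ratios: X/B = (X/P) × (P/B).

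**3. Heart rate record.** B = 80, P = 92 (Day 7), X = 108 (2.5 h).

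- Against baseline: 108/80 = 1.35, or +35%, which meets the endpoint.
- SAP 12.5.1: 108/92 = 1.17, or +17%, not flagged.
- SAP 12.5.2: 92/80 = 1.15, or +15%, not flagged.

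The limiting case is just under 25% on each rule: 1.25 × 1.25 = 1.5625. A rise of up to nearly 56% over baseline can therefore escape both. For a fall, 0.75 × 0.75 = 0.5625, so a fall of up to nearly 44% can. These are bounds, not expected sizes.

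**4. QTcF record.** B = 385, P = 395, X = 449 ms.

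- Against baseline: 449 − 385 = +64, which is over 60.
- SAP 12.6.1: 449 − 395 = +54, counted as 31 to 60.
- SAP 12.6.2: 395 − 385 = +10, not counted.
- Observed categories: 449 is below 451, not counted.

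In whole milliseconds, a rise of 61 or more over baseline must be at least 31 on one of the two change rules, because 30 + 30 = 60. With both readings present, such a rise is therefore under-classified and not lost from every change table. A rise of 31 to 60 ms over baseline can be lost altogether: 20 + 25 = 45 meets neither rule. If P is below B, the error runs the other way and the same-day rule flags too readily.

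**5. Regimens.** Dose times (SAP Appendix 1) are 0 h for QD, 0 and 12 h for BID, and 0, 7 and 14 h for TID. The next morning's pre-dose reading therefore falls 24 h, 24 − 12 = 12 h and 24 − 14 = 10 h after the last dose. The documents give no half-life. As an illustration only, assume a one-compartment model, absorption rate 1.5 per hour, and effect proportional to concentration. The Day 14 pre-dose effect, as a share of the largest effect at 2.5, 10.5 or 16.5 h, is then:

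| Assumed half-life | QD | BID | TID |
|---|---|---|---|
| 2 h | 0.001 | 0.039 | 0.078 |
| 6 h | 0.086 | 0.342 | 0.428 |
| 12 h | 0.295 | 0.586 | 0.655 |

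That share is what the same-day reference removes. The order is the same in each row; the size runs from negligible to large.

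**The case against.** The best defence is that same-day change is a legitimate summary of acute effect and removes day-to-day drift. There are also several safeguards. Observed QTcF categories apply at every intraday time point. Individual values are listed (SAP 9.1). Intraday QTcF boxplots are planned. ECG adverse events of Grade 3 or above enter the primary safety endpoint (Protocol 8.3.6). With complete data, the mean change from baseline at a post-dose time equals the sum of the intraday and daily mean changes, so the means are recoverable. The over-60 ms count is not itself a listed endpoint.

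Most of this stands, and it narrows the point. It does not remove it. Medians, spreads and participant counts do not add across tables, and the 25% count against baseline is a listed endpoint. SAP 12.5.1 and 12.5.2 have no absolute heart rate limit, and the orthostatic criteria in SAP 12.5.3 compare standing with supine, not with baseline. The grading table in Protocol Appendix 4 does treat a QTc rise of 0.06 s above baseline as Grade 3, but by Bazett's formula, and Protocol 8.3.6 leaves the investigator free not to follow it.

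A reader might infer that the plan hides large QTcF rises. That goes too far: a value of 465 ms, for example, enters the 451 to 480 category whatever the reference.

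A reader might also infer that more participants are missed on BID and TID, which would flatter those arms. The dose times support only a larger share of effect subtracted. The number missed also depends on how high each arm's peak is. In the same illustrative model at a 6 h half-life, the largest scheduled value is 336 units for 400 mg QD against 140 for 100 mg TID, so more of the 400 mg QD arm could lie near a threshold.

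**Conclusion.** The point holds as a mismatch between the stated endpoints and the tables meant to deliver them. The endpoints are defined against Day 1 pre-dose, but 12 of 15 post-dose time points per participant are never set against it. The 25% counts can miss changes outright, and the 31 to 60 and over-60 ms counts can miss or under-classify them. This rests only on the SAP's definitions and schedule and needs no pharmacokinetic assumption.

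How many participants would be affected cannot be stated. The documents give no half-life and no QTc effect size for TBA-7371, and Protocol 2.3 describes no QT signal in the first trial. Any percentage of missed QTcF events would come from assumed inputs. The same-day reference can remove a larger share of any drug effect for BID and TID than for QD, by an amount that depends on the unknown half-life. This is a reason to use a common drug-free reference. It does not show that the comparison favours those arms.

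**What to change.** In SAP 12.5.1 and 12.6.1, compute the change at every post-dose time point from the Day 1 pre-dose baseline of SAP 9.2, and apply the 25% criteria and the 31 to 60 and over-60 ms categories to that change. Let these readings count in the number of days with the criterion met (SAP 12.5.2). Keep same-day pre-dose change as a supplementary summary.

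The cost is SAP wording and a derived variable; no new data are needed. There are two downsides. Change from Day 1 includes day-to-day drift, which the retained same-day summary shows. Days 1, 4, 7, 10 and 14 would also contribute four readings to the day count, against one on other treatment days, so the table should say so.

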12.6.2 Daily ECG Results

Values of ECG variables (HR, QRS duration, RR, PR, QT, and QTcF intervals) measured at baseline (Day 1 predose), Days 4 (predose), 7 (predose), 10 (predose), 14 (predose), 15, 28, and 42 and changes from baseline will be summarized using descriptive statistics by treatment group.

Potentially clinically important criteria for QTcF are defined as follows:

- Observed: 451 to 480, 481 to 500, and >500 msec
- Change from baseline: 31 to 60, and >60 msec

For each of the criteria, the frequency and proportion (expressed in percent) of participants who met the criterion at each time point will be provided by treatment group. For the by-time point summary, the denominator for the proportion is the number of participants in the treatment group with non-missing values at baseline and the given post-baseline time point.

Additionally, values of ECG variables for sex subgroup (female and male) will be summarized similarly as described above. Boxplots of daily values of QTcF by treatment group and sex will be provided.

12.7 Clinical Safety Laboratory Measurement

Clinical safety laboratory parameters include:

Haematology	complete blood count [red blood cells (erythrocytes), haemoglobin, platelets and white blood cells (leukocytes)] and differential (absolute counts) including neutrophils, lymphocytes, monocytes, eosinophils and basophils.
Serum chemistry	alanine aminotransferase, aspartate aminotransferase, alkaline phosphatase, total bilirubin, blood urea nitrogen, creatinine, sodium, potassium.
Serum coagulation	prothrombin time, partial prothrombin time, international normalized ratio.
Urinalysis	specific gravity, pH, glucose, protein, blood, ketones, bilirubin, urobilinogen, nitrite, leukocyte esterase.

Clinical laboratory values for haematology, serum chemistry, coagulation, and urinalysis safety at baseline (screening), Days 3, 7, 14 and 42 changes from baseline will be summarized by treatment group using descriptive statistics. Changes may be assessed on the raw (difference) or

log (fold change) scale, depending on the whether the distribution of the measure is more appropriately described by a normal or lognormal distribution, respectively.

For urinalysis with categorical results, the frequency and proportion (expressed in percent) of participants will be tabulated for each category at baseline, Days 3, 7, 14, and 42 by treatment group. For the categorical urinalysis by-visit summary, the denominator for the proportion is the number of participants with non-missing values in the treatment group for the given parameter and time point.

Shift tables will be used to summarize haematology, serum chemistry, and coagulation laboratory values by treatment group. Shift tables will display transition of participants having lab values categorized as low, normal, or high with respect to their lab parameters reference ranges at baseline to normal, low or high at Days 3, 7, 14, and 42. For the by time point summary, the denominator for the proportion is the number of participants with non-missing values at baseline and the given time point in the treatment group for the given lab parameter.

All laboratory test results will be listed. The listings will include date and study day of collection. All units will be displayed in Système International units. Out of reference ranges values will be flagged in the data listings (e.g., 'L' or 'H').

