Assess the impact on heart rate, blood pressure and ECG profile of each dose regimen of TBA-7371 and of HRZE over the 14-day treatment period.	
From Day 1 through Day 15:
 
 Mean and frequency distribution of changes in HR, SBP and DBP as measured by the following 2 (BP) or 3 (HR) methods: 
 manual (vital signs), after at least 10 minutes in supine position (“manual, supine”); manual, after 2 (± 0.5) minutes in standing position (“manual, 2-min standing”); HR from ECG, supine position (“ECG, supine”) Frequency of participants with $\ge 25\%$ increase in HR, decrease in SBP, decrease in DBP vs. baseline as measured with any of the methods described above. Mean and frequency distribution of percentage of days with $\ge 25\%$ increase in HR, decrease in SBP, decrease in DBP vs. baseline. Mean/median change from screening through Day 15 in PR, RR, QRS, QT, QTcF values from baseline ECG.
Assess whether there is tachyphylaxis over the 14-day treatment period for HR, SBP, DBP and eye symptoms.	
 Mean change in HR, SBP and DBP from Day 1 to Days 4, 7, 10, 14 and 15 for each of the measurement methods described above. Change in frequency of participants with eye symptoms (all, severe, serious) and change in mean visual acuity score and frequency of color vision changes from Day 1 to Days 4, 7, 10, 14 and 15.
Assess whether cardiovascular and/or ophthalmic adverse events persist or recur up to 4 weeks after discontinuation of treatment with TBA-7371.	
 Mean change in HR, SBP and DBP from screening to Days 28 and 42 and from Day 14 to Days 28 and 42 for each of the measurement methods described above. Change in frequency of participants with eye symptoms (all, severe, serious) and change in mean visual acuity score and frequency of

Objectives	Endpoints
	color vision changes from screening to Days 28 and 42 and from Days 1-15 (combined) to Days 28-42 (combined).
Assess whether there are meaningful changes in safety laboratory measurement	For each blood/serum and urine parameter: 
 • Mean, median, highest and lowest value. • Shift tables from screening to Day 3, Day 7, Day 14 and Day 42.
Secondary, PK and PK/PD	

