See Section 10.6 (Appendix 6) for a list of commonly used prohibited medications (based on exclusion criteria # 11 to # 16). Please note that the list is not comprehensive and other medications with the features described below are also prohibited.

11. Use of medications active against Mtb within 3 months prior to the first dose of study drug.
12. Use of systemic immunosuppressive medications within 14 days prior to the first dose of study drug.
13. Use of strong inhibitors or strong inducers of cytochrome P450 (CYP) enzymes within 14 days prior to the first dose of study drug.
14. Use of inhibitors of phosphodiesterase (PDE) enzymes within 14 days prior to the first dose of study drug.
15. Use of medications known to affect the eye within 3 months prior to the first dose of study drug.
16. For HIV+ patients, use of medications listed in Section 10.6 (Appendix 6) within 3 months prior to the first dose of study drug.

Prior/Concurrent Clinical Study Experience

17. Participation in other clinical study(-ies) with investigational agent(s) within 6 months prior to trial start.

Diagnostic Assessments

18. The following laboratory values from blood collected during the Screening Phase, which represent Grade 2 or higher abnormalities per DAIDS Toxicity Table Version 2.1 (see Section 10.4, Appendix 4), will be cause for exclusion:
 - AST, ALT, alkaline phosphatase (ALP) \geq 2.5x upper limit of normal (ULN)

- Total bilirubin \geq 1.6x ULN
- Creatinine \geq 1.3x ULN
- Hemoglobin < 10 g/dL (male) or 9.5 g/dL (female)
- White Blood Cell Count (WBC) < 2,000 / mm³
- Platelets \leq 100,000 /mm³
- INR \geq 1.5x ULN
- PTT \geq 1.66 ULN
- PT \geq 1.25x ULN

ULN= upper limit of normal for local laboratory values

Grade 2 or higher abnormalities in other laboratory parameters from blood or urine Grade 1 abnormalities, or abnormalities from laboratory parameters not included in the DAIDS Toxicity Table Version 2.1, may lead to exclusion if the investigator considers them clinically significant.

Other Exclusion Criteria

19. History of allergy or hypersensitivity to any of the study drugs or related substances.
20. Positive urine drug screening for cocaine AND/OR amphetamines AND/OR opiates AND/OR methamphetamines. Note: screening will also be conducted for cannabinoids and results documented in the CRF; however, a positive test for cannabinoids is not an exclusion criterion.

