9.8 Visit Windows/Unscheduled Visits

Efficacy and safety analyses will use the nominal visits as collected in the study database, thereby, visit windows will not be applied.

Unscheduled visits will not be included in by-visit summaries or analysis, but may contribute to the baseline value and worst post-baseline assessments.

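### SAP 12.7 plans no graded or worst post-baseline laboratory summary: an ALT rise from DAIDS Grade 1 to Grade 3 can read as high to high, and post-baseline early-withdrawal, unscheduled and (read literally) Day 15 results reach no laboratory table

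*SAP*

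**What the plan says.** The objective in Protocol 3.2 is: "Assess whether there are meaningful changes in safety laboratory measurement". Its endpoints are the mean, median, highest and lowest values, and shift tables from screening to Days 3, 7, 14 and 42.

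SAP 12.7 provides by-visit descriptive statistics and changes from baseline (raw or fold change), shift tables for haematology, chemistry and coagulation, and a listing of all results flagged low or high. On the shift tables it says "Shift tables will display transition of participants having lab values categorized as low, normal, or high" against the reference range "at baseline to normal, low or high at Days 3, 7, 14, and 42". It plans no toxicity-grade table and no worst post-baseline laboratory summary.

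SAP 9.8 sets the visit rule: "Efficacy and safety analyses will use the nominal visits as collected in the study database", with no windows. It adds: "Unscheduled visits will not be included in by-visit summaries or analysis, but may contribute to the baseline value and worst post-baseline assessments". SAP 9.2 defines baseline: "The last assessment made prior to the first administered dose of study intervention will be considered baseline for analysis purposes".

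Protocol 8.3.4 schedules safety laboratory tests at screening and on Days 3, 7, 15 and 42, and at the Early Withdrawal Visit for anyone leaving between Day 1 and Day 14. It also allows extra tests at any time.

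**The concern.** A low/normal/high table cannot register worsening in someone who starts above the upper limit, and it cannot separate a trivial rise from a severe one in someone who starts normal. SAP 9.8 lets unscheduled values contribute to worst post-baseline assessments, but SAP 12.7 defines none for laboratory data, so that permission has no effect there. Early-withdrawal results fall outside the named days.

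At stake is an objective answer to whether meaningful laboratory changes occurred. Protocol 2.3 names hepatitis among the common AEs of the comparator, so liver tests are a natural place to look. Without a programmed grade count, the number of participants reaching Grade 3 or 4 is known only through AEs that open-label investigators chose to record.

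**Working it through.** The plan gives no figure to reproduce on this point. The check classifies ALT under both schemes and then traces each type of result to its outputs.

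**Inputs.** Criterion 18 in Protocol 5.2 excludes ALT at 2.5 x ULN or more. DAIDS cut-offs for ALT in Protocol Appendix 4 (x ULN) are: Grade 1, 1.25 to <2.5; Grade 2, 2.5 to <5.0; Grade 3, 5.0 to <10.0; Grade 4, 10.0 or more. The SAP category is high if the value exceeds ULN, assuming ULN is the top of the reference range.

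**Step 1: classify eligible baselines.**

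| Baseline (x ULN) | Later (x ULN) | Fold | SAP shift | DAIDS grade |
|---|---|---|---|---|
| 2.0 | 1.5 | 0.75 | high to high | 1 to 1 |
| 1.3 | 9.0 | 9.0/1.3 = 6.9 | high to high | 1 to 3 |
| 2.49 | 5.0 | 5.0/2.49 = 2.01 | high to high | 1 to 3 |
| 1.1 | 9.9 | 9.9/1.1 = 9.0 | high to high | below 1 to 3 |
| 1.3 | 12 | 12/1.3 = 9.2 | high to high | 1 to 4 |
| 0.8 | 1.5 | 1.5/0.8 = 1.9 | normal to high | below 1 to 1 |
| 0.8 | 9.9 | 9.9/0.8 = 12.4 | normal to high | below 1 to 3 |

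Eligible baselines lie below 2.5 and Grade 3 starts at 5.0, so any rise to Grade 3 is more than 5.0/2.5 = 2-fold. In the shift table it is indistinguishable from an improvement (high baseline) or from a Grade 1 rise (normal baseline).

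**Step 2: trace each result.**

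- *Days 3, 7 and 42:* by-visit statistics, shift table and listing. SAP 9.1 includes minimum and maximum, so an extreme value is visible, but not as a number of participants by grade.
- *Pre-dose repeat:* can become baseline under SAP 9.2 and 9.8, and so can enter the tables.
- *Post-baseline unscheduled test:* barred from by-visit summaries, with no worst-value laboratory output to enter. Listing only.
- *Early Withdrawal Visit:* not a tabulated day. Listing only. After Day 7 the next scheduled safety sample is Day 15, so for someone leaving after Day 7 and before the end of treatment, the Day 3 and Day 7 results are tabulated but the last on-study result is not.
- *Day 15:* Protocol 8.3.4 schedules the end-of-treatment sample on Day 15. Protocol 3.2 and SAP 12.7 name Day 14. With nominal visits and no windows, a sample stored as Day 15 has no column.
- *Any result judged clinically significant:* recorded as an AE and tabulated by intensity (SAP 12.1.2.1). If Grade 3 or higher from Day 1 through Day 15, it also enters the primary safety table (SAP 12.1.1).

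**Step 3: compare with other safety data.** SAP 12.3 and 12.4 define worst values over Days 1 to 15 for visual acuity and color vision. SAP 12.5 and 12.6 count participants crossing set thresholds for vital signs and QTcF. Laboratory data have neither. SAP Table 2 lists highest and lowest values with no visit attached, while SAP Table 4 and 12.7 tie the summaries to named days.

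**The case against.** The strongest reply is that SAP 12.7 delivers the by-visit shift tables that Protocol 3.2 asks for, and nothing in the protocol promises graded shifts. Continuous summaries cover every participant with a tabulated result, including those raised at entry. All results are listed and can be read for 90 participants, and the IDMC reviews safety laboratory tests (Protocol 9.7.1). Withdrawal is expected to be uncommon (Protocol 7.2), and Grade 1 abnormalities at screening may exclude if the investigator finds them clinically significant. All of this stands, and it makes the point one of improvement rather than of a broken promise.

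Three stronger readings are tempting and are not supported:

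- *Early-withdrawal and repeat results enter no table at all.* They can enter the AE tables, and a pre-dose repeat can become baseline. The gap is confined to post-baseline results and laboratory tables.
- *The participants at most risk are left out.* They are included at the tabulated visits. What is lost is the grade, the count and the off-schedule result.
- *One missed Grade 3 case shifts a regimen by 1/15 = 6.7 percentage points.* That is arithmetic on one hypothetical participant. The laboratory tables do not feed the primary endpoint.

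The AE route still does not close the gap. Protocol 8.3.4 leaves clinical significance to the investigator, who need not follow the DAIDS grades, and site staff know the treatment. The listing carries low/high flags, not grades.

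**Conclusion.** The concern holds in this limited form. SAP 12.7 has no summary that counts participants by laboratory toxicity grade or takes their worst post-baseline value. A rise of more than 2-fold to Grade 3 ALT can therefore appear as no shift, and post-baseline early-withdrawal and unscheduled results are absent from every laboratory summary. The Day 14 and Day 15 references must be reconciled.

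The number affected cannot be estimated: the documents give no frequency of raised ALT at entry, of retesting, or of abnormalities found only at early withdrawal. The Day 15 gap assumes that the database labels that sample Day 15. This is a worthwhile, low-cost improvement for a secondary objective and does not alter the primary safety analysis.

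**What to change.** Add to SAP 12.7, by treatment group:

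1. A shift table from baseline DAIDS grade to worst post-baseline DAIDS grade through Day 15, derived by program and including Early Withdrawal Visit, unscheduled and Day 15 results.
2. A count of participants with any Grade 3 or 4 value, whether or not it was reported as an AE.

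Specify the grading rules. Limit the table to parameters graded in Protocol Appendix 4; BUN, monocytes, eosinophils and basophils, for example, have no grades there. Grade high and low sodium and potassium separately. State whether creatinine is graded by ULN, by change from baseline, or by the higher of the two. The choice matters: a rise from 0.5 to 0.8 x ULN is 0.8/0.5 = 1.6-fold, which is Grade 3 by the baseline rule while still below ULN. Appendix 4 carries a reminder to take the higher grade, so the SAP should say whether it follows it.

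Reconcile Day 14 in Protocol 3.2 and SAP 12.7 with Day 15 in Protocol 8.3.4, and say which nominal visit fills the end-of-treatment column.

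The cost is modest programming plus the parameter-specific rules above. No new data are needed.
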